4.9 Safety Analyses

Safety results (AEs, vital signs, physical examinations, laboratory, ECG) will be compared between the Nanocort arms and the Depo-Medrol arm. Shift tables and shift plots will be used to evaluate changes in clinical laboratory test results at different time points compared to Baseline values. Proportion of patients whose test values are outside specific ranges will also be presented. All abnormalities in physical examination, ECG and vital signs will be presented.

No formal hypothesis testing of safety data will be undertaken; however, the data summaries will be examined for any trends amongst the dose levels.

4.9.1 Laboratory Results

Hematology, chemistry and urinalysis analysis test results in SI units will be summarized by lab test, treatment group and time point. For hematology, chemistry and urinalysis tests, changes from baseline will be included in these tables.

Abnormality findings i.e. normal, abnormal, not clinically significant (NCS) or abnormal, clinically significant (CS) will be summarized by lab test, treatment group and time point.

Shift tables will be provided for each lab test with baseline value (low, normal, high) for each treatment group across the top and the time point value (low, normal, high) along the side.

4.9.2 Vital Signs

Vital sign results and absolute changes from baseline for systolic blood pressure, diastolic blood pressure, heart rate, respiration rate and body temperature will be summarized by treatment group and time points.

4.9.3 Physical Examinations

The complete and abbreviated physical examination results will be tabulated by treatment group and time points. The number and percentage of subjects with normal, abnormal, not clinically significant and abnormal, clinically significant results will be given.

4.9.4 ECG

The number and percentage of subjects with clinically significant results will be summarized by treatment group and time point.

4.9.5 Concomitant Medications

The number and percentage of subjects with *at least* one concomitant medication (CM) and one CM given for AE will be tabulated by treatment and overall. Concomitant medication will be coded by the WHODD coding dictionary version June 2015.

4.9.6 Adverse Events

The number and percentages of subjects with different AEs will be tabulated with MedDRA System Organ Class (SOC) and Preferred Term (PT) by treatment and overall. If a subject had more than one AE for a particular SOC, he/she will be counted only once for that SOC. If a subject had more than one AE for a particular PT, he/she will be counted only once for that PT. In addition, summary tables will include occurrence rates for:

- AE,
- SAE
- Severe AE
- AE related to IM injection
- SAE related to IM injection
- AE related to IV infusion
- SAE related to IV infusion
- IM injection related AE leading to drug withdrawal
- IV infusion related AE leading to drug withdrawal
- AE leading to death
- AE leading to concomitant medication
- AE starting during IV infusion
- AE starting within 24 hrs of end of IV infusion
- AE requiring treatment given.

Adverse events will be coded by the MedDRA coding dictionary, version 19.

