5.1.3 Blinding

The study will be performed in a double blind, double dummy fashion. Each patient will receive an infusion and an IM injection containing either an active treatment or a dummy treatment. Opaque IV lines, sleeved bags and opaque syringes will be used to maintain blinding. The IMP preparation will be done by an independent unblinded person (pharmacist or designated person) in order to keep the Investigator and other site personnel blinded.

Proper care has to be taken so that the patient's treatment will not be disclosed to the patient, Investigator or other site personnel.

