9.2 AEs, SAEs and SUSARs

9.2.1 Adverse events (AEs)

An adverse event (AE) is any untoward medical occurrence in a subject who has received study drug, or any untoward or unintended response to an experimental intervention which does not necessarily have a causal relationship with the treatment. Adverse Events include:

- Any new undesirable medical experience or an unfavourable and unintended change of an existing condition that occurs during or after treatment.
- Untoward clinically significant manifestations of laboratory abnormalities (e.g., clinical chemistry, haematology, urinalysis, etc.) or other abnormal assessments (e.g., electrocardiogram, vital signs) independent of the underlying medical condition. If possible, abnormal laboratory findings with these characteristics should be reported as a clinical diagnosis rather than the abnormal value itself (e.g., "anemia" rather than "decreased blood count").

Situations where an untoward medical occurrence has not occurred (e.g., hospitalisation for elective surgery, social and/or convenience admissions) do not represent AEs.

Subjects will be carefully monitored throughout the study for AEs. At each study visit, subjects will be asked to report any AE. All AEs are followed until they are resolved or stabilized, or until all attempts to determine resolution of the event are exhausted. The investigator will use his/her discretion in ordering additional tests as necessary to monitor the resolution of such events.

Each collected AE, regardless of the relationship to study drug, will be recorded in the AE eCRF. All entries should contain an event term, date of onset, date of resolution, severity, action taken, outcome, relationship to study drug, and a seriousness assessment. The investigator will document all AEs in the subject's source document.

Severity will be assessed by Investigator according to the following definitions:

Mild: The event is of little concern to the subject and/or of no clinical significance. The event is not expected to have any effect on the subject's health or wellbeing.

Moderate: The subject experienced discomfort enough to cause interference with usual activity, and/or the condition required specific treatment. The event is of some concern to the subject's health or wellbeing. The event may require medical intervention.

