- **Related:** The event follows a reasonable temporal sequence from administration of the drug; that follows a known or expected response pattern to the suspected drug; that is confirmed by stopping or reducing the dosage of the drug; and that is not explained by any other reasonable hypothesis.

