2.4 Safety Population

The safety population (SAF) will include all patients who receive at least one infusion or part of infusion with Nanocort/placebo or at least one IM injection or

part of IM injection with Depo-Medrol/placebo and had at least one post baseline safety assessment.

Patients will be assigned to treatment groups as treated for analysis.

3. Blinded Review of the Data

A blinded data review will be held before breaking the blind. The blinded data review will be performed by at least the Principal Investigator, the Medical Monitor, the Study Lead and the Trial Statistician. The goal of the blinded data review is to determine for each subject the maintenance of improvement at 12 Weeks, the protocol violations and to evaluate the impact of these protocol violations on the EULAR response.

The decisions taken during the blinded data review will be finalized and signed by participants on the blinded data review report before unblinding.

4. Statistical and Analytical Methods

This analysis plan gives a detailed description of the statistical methodologies, data listings, and summary tables planned in the analysis of the data in the CLR-15-05 study. This section describes the statistical analyses of the study based on the statistical section of the protocol (CLR15_05_Prot_V3.1_Amend_25Sep2017.pdf). Any difference with the protocol will be identified and documented. The statistical data analysis, described in this document, is intended to provide unbiased and valid conclusions concerning the objectives of the study.

This SAP describes only the analyses for the study objectives not involving the PK objectives. The PK objectives will be described in a separate analysis plan.

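### SAP 4.9.6 reports treatment-related AEs only by route (IM or IV); it needs rows for AEs related to study treatment by either route

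*Combined protocol and SAP*

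**What the plan says.** SAP 4.9.6 lists 14 AE summary rows. Six depend on causality, and all six are tied to a route. There is a row for "AE related to IM injection" and one for "AE related to IV infusion", a matching pair for SAEs, and a pair for withdrawals, such as "IM injection related AE leading to drug withdrawal". No row combines the routes. The other eight rows do not depend on causality. Separately, AEs are "tabulated with MedDRA System Organ Class (SOC) and Preferred Term (PT) by treatment and overall". For the safety population, SAP 2.4 states: "Patients will be assigned to treatment groups as treated for analysis".

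Protocol 9.2.1 describes one causality item per event. The eCRF entry contains, among other fields, "relationship to study drug, and a seriousness assessment", judged by the investigator on five levels (not related, unlikely, possibly, probably, related). It mentions no judgement by route. The SAP does not say which levels count as related.

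On treatment, protocol 5.1.3 says: "Each patient will receive an infusion and an IM injection containing either an active treatment or a dummy treatment". The investigator and other site staff are blinded.

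**The concern.** The safety question is what each product does compared with Depo-Medrol, and this comparison is part of the primary objective. For that, a reader of the AE summary wants one line: subjects with at least one AE judged related to study treatment, by arm. The plan does not provide it. It asks a blinded investigator which of two same-day administrations caused an event, when one of them is saline and both active products are glucocorticoids. For a systemic event there is no sound basis for that choice.

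The withdrawal rows have the same limitation. SAP 1.4.3 lists AEs leading to withdrawal as an endpoint without reference to route, yet 4.9.6 tabulates them only as IM-related or IV-related.

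The SAP also departs from the protocol without saying so. SAP section 4 undertakes to identify and document any difference from the protocol, but the modifications in SAP 4.11 do not mention the move from one causality item to two.

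**Working it through.** The plan states no figure on this point, so there is nothing to reproduce. The check is a row count, a bound, and an illustration with assumed rates, because the documents give no related-AE rates.

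**1. Row count (SAP 4.9.6).** Of the 14 rows, 3 are IM-related, 3 are IV-related and 0 are for either route. The remaining 14 − 6 = 8 do not depend on causality. They cover all AEs, SAEs, severe AEs, deaths, two rows on treatment given for the event, and two on timing relative to the infusion.

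**2. Can the either-route count be recovered?** Let a and b be the proportions of subjects in one arm with an IM-related and an IV-related AE. A subject may be in both rows, so

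max(a, b) ≤ proportion related to either route ≤ min(a + b, 100%).

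- Assume a = b = 10% in an arm of the planned size, 110 (protocol 4.4). That is 11 subjects in each row. The either-route count is between 11 (10%) and 22 (20%).
- Assume a = 20% and b = 5%. The either-route rate is between 20% and 25%.

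The two rows fix the answer only if the overlap is known, and the summary does not show it.

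**3. Can arms be compared within or across rows?** Assume true rates of systemic related AEs of 20% (Nanocort) and 30% (Depo-Medrol), one such event per affected subject, each event ascribed to a single route, and a share p ascribed to IV in every arm. Then:

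- IV row: 20% × p against 30% × p.
- IM row: 20% × (1 − p) against 30% × (1 − p).
- Active-product cells: Nanocort in the IV row, 20% × p; Depo-Medrol in the IM row, 30% × (1 − p).

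| p | IV row (Nanocort / Depo-Medrol) | IM row (Nanocort / Depo-Medrol) | Active-product cells (Nanocort / Depo-Medrol) |
|---|---|---|---|
| 0.3 | 6% / 9% | 14% / 21% | 6% / 21% |
| 0.5 | 10% / 15% | 10% / 15% | 10% / 15% |
| 0.7 | 14% / 21% | 6% / 9% | 14% / 9% |

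Within a row the ratio stays at 20:30, but each row mixes an active product in one arm with saline in another, and the absolute difference shrinks by the assumed share. Comparing the active-product cells means reading across rows. The result then depends on p: the cells are equal where 20p = 30(1 − p), that is p = 0.6, and above that the order reverses.

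**4. If both routes are marked.** If the investigator marks a systemic event as related to both routes, the active-product cell loses nothing. The loss in step 3 therefore depends on events being ascribed to the dummy alone.

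**5. Is the addition feasible?** The eCRF is not among the documents. If it holds one causality item, as protocol 9.2.1 describes, the either-route row comes directly from it and the six route rows cannot be derived. If it holds two, the either-route row is their union. The SAP needs correcting in both cases.

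**The case against.** The case against is substantial, and much of it stands.

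- Columns are by treatment, and subjects are grouped as treated. The IV row under Nanocort and the IM row under Depo-Medrol therefore do count AEs attributed to the active product. A reader might infer that no row counts events related to the treatment actually given. That is not so; those counts may be incomplete, and they lie in different rows.
- Some events can be attributed while blinded. Injection-site events and reactions during the infusion are linked to a route by site and timing, and infusion reactions are the risk that the protocol singles out for Nanocort. Two further rows, for onset during the infusion and in the 24 hours after it, need no causality judgement. The difficulty is confined to systemic events.
- A reader might infer that each row must understate the active product's count. As step 4 shows, that is conditional, and nothing in the documents shows how often the dummy alone would be named.
- The all-cause AE, SAE and severe AE rows and the SOC/PT tables by arm are unaffected. They carry the main safety comparison in a blinded randomised trial. Individual AEs are listed, no formal safety testing is planned, and the SAP does not say that its list of rows is exhaustive.
- A reader might also fault the protocol's top causality level, which describes an event "that is confirmed by stopping or reducing the dosage of the drug", as hard to meet after a completed administration. That would remove events only if the SAP counted that level alone as related. Nothing says it does, and the levels possibly and probably related carry no such condition. The gap is an unstated cut-off.

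What survives is the missing either-route row, the unreliable route split for systemic events, the undefined cut-off, and the undocumented difference from the protocol's single causality item.

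**Conclusion.** The point holds in this limited form. All six causality rows in SAP 4.9.6 are route-specific, blinded route attribution is unreliable for systemic events, and the drug-related AE rate per arm cannot be recovered from the rows. With 11 subjects in each route row, the either-route count could be anything from 11 to 22. No single row compares drug-related AEs like with like, because the active product is in the IV row for Nanocort and the IM row for Depo-Medrol.

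The consequence is modest. Causality rows are one part of a descriptive safety summary whose all-cause tables stand. The percentages rest on assumed rates, and step 3 also on single-route attribution with the same share in every arm. The arm size of 110 is the planned one; the study ended early with far fewer subjects than planned, so actual counts will be smaller, but the bound applies at any size.

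**What to change.** Change the SAP only.

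1. In 4.9.6, add three rows as the main causality summary: AE, SAE, and AE leading to drug withdrawal, each related to study treatment by either route, counting each subject once per row.
2. In the same section, define related as possibly, probably or related on the protocol 9.2.1 scale.
3. Keep the route-specific rows as supportive, chiefly for injection-site and during-infusion events, and state from which eCRF item or items they are derived.
4. In 4.11, record that the SAP reports causality by route whereas the protocol describes a single relationship to study drug.

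The cost is three table rows and a few sentences, using data already collected, with no burden on patients or sites. Rewriting the causality scale in protocol 9.2.1 is not proposed: the study has been conducted and was terminated early, so a new definition would not alter judgements already recorded.

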NSAIDs	Non-steroidal anti-inflammatory drugs
PE	Physical examination
PEG	Polyethylene glycol
PI	Principal Investigator
PK	Pharmacokinetic(s)
PLP	Prednisolone sodium phosphate
PP	Per protocol
PRO	Patient Reported Outcome
PV	Pharmacovigilance
QA	Quality Assurance
QoL	Quality of Life
RA	Rheumatoid Arthritis
RBC	Red blood cells
RF	Rheumatoid Factor
SAE	Serious Adverse Event
SAF	Safety
SAP	Statistical analysis plan
SD	Standard deviation
SF-36	Short Form 36
SGOT	Serum glutamic oxaloacetic transaminase
SGPT	Serum glutamic pyruvic transaminase
SLE	Systemic lupus erythematosus
SPC	Summary of Product Characteristics

SUSAR	Suspected Unexpected Serious Adverse Reaction
VAS	Visual Analogue Scale
WBC	White blood cells

SUMMARY

Rationale:

Inflammatory disorders, such as rheumatoid arthritis (RA), are chronic, progressive, and debilitating diseases that often lead to disability. Adequate treatment is difficult and costly, and hospitalization often occurs [1]. Prednisolone and some other glucocorticoids (GCs) can be highly effective in treating joint inflammation, but their systemic application is limited because of a high incidence of serious adverse effects, especially related to long-term treatment [2, 3]. Besides a poor safety profile, also poor localization in inflamed areas in the body limits the usefulness of glucocorticoids in the patient [4]. Prednisolone sodium phosphate (PLP) encapsulated in long-circulating liposomes (Nanocort®) is being developed with the prospect of providing enhanced localized exposure over existing systemic formulations of glucocorticoids in certain “flare-ups” of inflammatory diseases that currently benefit from prednisolone administrations. As a result, Nanocort might be able to significantly reduce frequency of administration and use of the glucocorticoids compared to the treatment with intramuscular (IM) corticosteroids and so has a safety advantage.

This study is designed to evaluate the safety and efficacy of intravenous (IV) polyethylene-glycosylated (PEG)-liposomal prednisolone sodium phosphate (Nanocort) in RA subjects with flare/exacerbation.

Objective:

Primary objective: To assess efficacy and safety (treatment of signs and symptoms) of Nanocort in subjects with active rheumatoid arthritis who are experiencing a flare/exacerbation in comparison to a standard of care medication (Depo-Medrol).

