8.1.2 Key Secondary study parameters/endpoints

- EULAR responder (only good) rate at Week 1 (Day 8)
- EULAR responder (moderate and good combined) rate at Week 2 (Day 15)
- EULAR responder (only good) rate at Week 2 (Day 15)

Secondary study parameters/endpoints

The secondary endpoints that will be measured are:

- EULAR response at Week 1, 2, 3, 4, 6, 8 and 12
- DAS28 mean and % change at Week 1, 2, 3, 4, 6, 8 and 12
- Time to first EULAR response (moderate/good)
- ACR 20/50/70 response scores at Week 1, 2, 3, 4, 6, 8 and 12
- Tender joint counts at Week 1, 2, 3, 4, 6, 8 and 12
- Swollen joint counts at Week 1, 2, 3, 4, 6, 8 and 12
- Patient pain and Global Visual Analog Score (VAS) score at Week 1, 2, 3, 4, 6, 8 and 12
- Investigator Global Visual Analog Score (VAS) score at Week 1, 2, 3, 4, 6, 8 and 12
- Short Form 36 (SF-36) to assess physical and mental component at Week 1, 2, 4, 6, and 12.
- Health Assessment Questionnaire (HAQ) at Week 1, 2, 3, 4, 6, 8 and 12.
- The Functional Assessment of Chronic Illness Therapy (FACIT) at Baseline, Week 4 and 6
- Health Economics Questionnaire at Week 12

- Maintenance of Improvement at 12 Weeks assessed during a blinded review by the Medical Monitor (MM) and Principal Investigator (PI) at the end of the study
- AEs (including glucocorticoid related AEs, AEs leading to withdrawal, AEs leading to discontinuation of medication, and AEs due to infusion reactions)
- Vital signs
- Physical examinations
- Laboratory
- ECG
- [REDACTED]
- [REDACTED]
- Assessment by monitoring cortisol levels at Screening, Baseline, 6 and 12 weeks

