1.4.3 Secondary Endpoints

- EULAR response at Week 1 (Day 8), Week 2 (Day 15), Week 3, 4, 6, 8 and 12
- DAS28 mean and % change from baseline at Week 1, 2, 3, 4, 6, 8 and 12
- Time to first EULAR responder (moderate/good)
- ACR 20/50/70 response scores at Week 1, 2, 3, 4, 6, 8 and 12
- Tender joint counts at Week 1, 2, 3, 4, 6, 8 and 12
- Swollen joint counts at Week 1, 2, 3, 4, 6, 8 and 12
- Patient pain and Global Visual Analog Score (VAS) score at Week 1, 2, 3, 4, 6, 8 and 12
- Investigator Global Visual Analog Score (VAS) score at Week 1, 2, 3, 4, 6, 8 and 12

- Short Form 36 (SF-36) to assess physical and mental component at Week 1, 2, 4, 6 and 12
- Health Assessment Questionnaire (HAQ) at Week 1, 2, 3, 4, 6, 8 and 12.
- The Functional Assessment of Chronic Illness Therapy (FACIT) at Baseline, Week 4 and 6
- Health Economics Questionnaire at Week 12
- Maintenance of Improvement at 12 Weeks assessed during a blinded review by the Medical Monitor and PI at the end of the study, before database lock
- Pharmacokinetics (PK) assessment in subset of patient population at Baseline, Week 1, 2, 3, 4 and 6
- AEs (including glucocorticoid related AEs), AEs leading to withdrawal, AEs leading to discontinuation of medication, and AEs due to infusion reactions)
- Vital signs
- Physical examinations
- Laboratory
- ECG
- Assessment by monitoring cortisol levels at Screening, Baseline 6 and 12 - weeks

2. Analysis Populations

Analysis of safety data will be based on the safety population (SAF). The primary analysis population for efficacy will be the Intent-to-Treat (ITT) population. Analysis of primary efficacy endpoint and key secondary endpoints will also be performed on the Per-Protocol (PP) population to confirm the findings from the ITT population.

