4.5 Patient Disposition

The number and percentage of subjects allocated to each of the populations will be summarized for all enrolled subjects. The number and percentage of subjects completing the study, discontinued, the reasons of discontinuation and the study duration (end of study date-date of first treatment +1) will be tabulated overall and by treatment.

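### SAP 4.9.6 summarises AE-related drug withdrawal only for route-related events, has no row for AEs leading to study withdrawal, and neither defines nor summarises glucocorticoid-related AEs, although all three are named safety endpoints

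*Combined protocol and SAP*

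**What the plan says.** The SAP's list of secondary endpoints (1.4.3) contains this item: "AEs (including glucocorticoid related AEs), AEs leading to withdrawal, AEs leading to discontinuation of medication, and AEs due to infusion reactions". Protocol 8.1.2 has the same four components with a bracket placed differently: "AEs (including glucocorticoid related AEs, AEs leading to withdrawal, AEs leading to discontinuation of medication, and AEs due to infusion reactions".

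SAP 4.9.6 sets out the AE reporting. It begins with a general tabulation, shown for each arm and for all arms together: "The number and percentages of subjects with different AEs will be tabulated with MedDRA System Organ Class (SOC) and Preferred Term (PT". It then lists 14 occurrence-rate rows. Two of them concern withdrawal: "IM injection related AE leading to drug withdrawal" and "IV infusion related AE leading to drug withdrawal".

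On data collection, Protocol 9.2.1 states: "Each collected AE, regardless of the relationship to study drug, will be recorded in the AE eCRF". The action taken is one of the items recorded for each event, and discontinuation of study drug is one of its categories. Outside the AE section, SAP 4.5 will tabulate the following by treatment: "The number and percentage of subjects completing the study, discontinued, the reasons of discontinuation and the study duration".

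The opening of SAP section 4 undertakes to identify and document any difference from the protocol. SAP 4.11, which lists the modifications, does not mention AE endpoints.

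**The concern.** The endpoint is named without regard to cause, while the planned summary is conditional on cause. An all-causality count of AEs that stop treatment is a basic tolerability measure because it does not depend on an investigator's attribution. Replacing it with events judged related to one route gives a narrower quantity under a similar label.

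The glucocorticoid component bears directly on the product's rationale. The protocol Summary argues that Nanocort may reduce glucocorticoid use "compared to the treatment with intramuscular (IM) corticosteroids and so has a safety advantage". Safety is also part of the primary objective (Protocol section 2, SAP 1.3.1). Yet the summary that would speak most directly to this rationale has no definition and no row. If nothing is added, a reader of the AE summary will not find two of the named components, will find a third only as a subset, and will not be told that the plan changed.

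**Working it through.** No arithmetic figure is at issue, because safety is descriptive. The check sets the named components against what the SAP plans to produce.

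**Row count in SAP 4.9.6.** All-cause rows for AE, SAE and severe AE (3); AE and SAE related to each route (4); route-related drug withdrawal (2); death (1); concomitant medication or treatment given (2); timing relative to the infusion (2). Total 3 + 4 + 2 + 1 + 2 + 2 = 14.

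| Named component | Row in SAP 4.9.6 | Elsewhere in the SAP |
|---|---|---|
| AE leading to withdrawal | None for leaving the study | SAP 4.5 reasons for discontinuation; categories not listed |
| AE leading to stopping medication | Two rows, each limited to AEs related to one route | Dose administration Tables 5 to 7; Listings 7.D, 21.A and 21.B |
| Glucocorticoid-related AE | None, and no definition in either document | Individual terms in the table by organ class and preferred term; laboratory summaries (SAP 4.9.1) |
| Infusion reactions | IV-related rows and two timing rows | Not needed |

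Three of the four components are therefore incomplete or absent in the AE summary.

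**Does disposition close the gap?** Only in part. Protocol 8.5 lists AEs among the reasons for which subjects may be discontinued, so an AE category in SAP 4.5 is likely, though not stated. But Protocol 8.5 and 8.6 also keep subjects with incomplete drug administration in the study for all planned visits. Someone who stops drug because of an AE and continues follow-up is not a study discontinuation and would not appear there.

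**Do the two drug-withdrawal rows cover study withdrawal?** No. Dosing is on Day 1 and Day 15 only, with follow-up to Week 12. After the second dose there is no study drug left to withdraw, so an AE that ends participation later fits neither row even if judged related.

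**Is the relatedness filter well defined?** Protocol 9.2.1 grades causality on five levels against study drug. SAP 4.9.6 splits it by IM and IV route and does not say which levels count as related. Every arm receives saline by one route (Protocol 7.3), so a blinded investigator has to attribute a systemic effect to one of two administrations without knowing which was active.

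**Can the missing rows be produced?** Yes for drug discontinuation, from the action taken, which is recorded for every AE. For study withdrawal, Protocol 8.5 requires the reason to be recorded; whether the eCRF links it to a specific AE is not stated. For glucocorticoid-related AEs, the entries listed in Protocol 9.2.1 include no such flag, so a term list is needed.

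**The case against.** The strongest reply is that little information is lost. Every AE, whatever its causality, appears by organ class and preferred term, and there are all-cause rows for AE, SAE and severe AE. Listings 7.D and 21 carry discontinued doses and events subject by subject. Laboratory tests relevant to glucocorticoid exposure (glucose, HbA1c, lipids, osteocalcin, cortisol) are summarised by arm with shifts. The row list is not stated to be exhaustive, and Tables 25.A and 25.B appear only as titles, so additional rows cannot be ruled out. All of this stands. What is missing is the all-cause link between an AE and stopping drug or leaving the study, together with the glucocorticoid grouping. A list that names route-specific withdrawal rows but not the all-cause ones does not commit the analyst to the named endpoint.

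Four stronger readings are tempting, and the documents do not support them:

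- A reader might infer that an unrelated AE ending participation is counted nowhere. It is counted in the all-AE tabulations and may be counted in disposition; it is absent only from the withdrawal rows.
- A reader might want to state by how much discontinuation is understated. Neither the rate of AE withdrawals nor the share judged unrelated is given, so any figure would only restate an assumption.
- A reader might infer that glucocorticoid terms will be chosen after unblinding. The documents are silent on when or whether they would be chosen; that silence is a gap, not a stated plan.
- A reader might ask for a risk difference with a confidence interval. SAP 4.9 plans no formal testing of safety data, and reporting the named endpoint does not require one.

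**Conclusion.** The point holds as a reporting gap that should be closed before unblinding. The AE summary would present a related-only subset of the named drug-discontinuation endpoint, no count of AEs leading to study withdrawal, and no defined glucocorticoid-related category, and SAP 4.11 does not declare the departure. Disposition is a partial substitute for study withdrawal and none for subjects who stop drug but stay in follow-up.

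The size is three of four named components. The number of subjects affected cannot be derived from the documents. With two doses per subject and a sample reduced by early termination, few drug discontinuations are likely. The conclusion rests on reading the row list in SAP 4.9.6 and the table titles in SAP section 7 as the intended content. Alpha, power and the efficacy result are unaffected.

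**What to change.** In SAP 4.9.6 and Table 25.A, each as n (%) by arm:

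1. Add *AE leading to discontinuation of study drug*, any causality, derived from the recorded action taken. State whether the category for drug stopped and then restarted is included.
2. Add *AE leading to study withdrawal*, any causality, and make it agree with the AE reason in the SAP 4.5 disposition table.
3. Keep the two existing route-related rows as subsets of row 1, and state which causality levels count as related.
4. Add *Glucocorticoid-related AE*, defined by a MedDRA preferred-term list signed at the blinded data review described in SAP section 3.

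If the sponsor prefers not to add a row, SAP 4.11 should record the omission and the reason.

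The cost is three table rows and one term list agreed at a meeting already planned. The drug-discontinuation and glucocorticoid rows need no new data. The study-withdrawal row uses the recorded reason for withdrawal, with a check of whether it can be tied to a specific AE.
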